### **6.2 Analysis Cohorts**

222223

- 224 Primary and Secondary Analyses:
- All randomized participants and periods will be analyzed according to the ITT principle as described above.
- All participants with at least 72hr of CGM data in at least one randomized period will be included in the CGM-based analyses.
- All randomized periods with a HbA1c measurement at 13 weeks will be included in HbA1c analyses. Similar approaches will be followed for the other secondary outcomes like insulin, weight/BMI, and questionnaires analyses.

232

233

235

236

237

238

239

- Per Protocol (PP) Analyses:
- Three different per protocol analyses will be considered:
  - If more than 10% of participants have fewer than 168 hours CGM data in either treatment period, the primary and secondary hierarchical analyses will be replicated excluding such participants.
  - The primary and secondary hierarchical analyses will be replicated restricting to participants who:
    - ➤ used the system in CL mode for >80% (i.e. >1,613 hours) during the MPC period, and
    - ➤ used the sensor for >80% (i.e. >1,613 hours) during the SAP period.

240241

- 242 Safety Analyses:
  - Safety outcomes will be reported for all randomized participants by period. Separately, any reported adverse events pre-randomization will be tabulated.

245

246

243

244

- Sensitivity Analysis:
- Missing Data: As noted below in Section 6.2, all participants with ≥72hr of CGM data in at least one of the two crossover periods will be included in primary analyses. It is also worth emphasizing that any statistical method for handling missing data makes untestable assumptions. The goal will be to minimize the amount of missing data in this study so that results and conclusions will not be sensitive to which statistical method is used. To that end, sensitivity analyses will be performed to explore whether results are similar for primary and secondary hierarchical analysis when using different methods. The following methods will be applied:
  - Available cases participants with ≥72hr of CGM data in at least one of the two crossover periods (this is the default method)
  - o Complete cases only participants with ≥72hr of CGM data in both crossover periods
  - o Rubin's multiple imputation

257258

254

255

- Carry-over Effect: As noted in Section 7 below, the model will include pre-randomization baseline, the two crossover periods, and will adjust for period and site (as random effect). A model will be run for the primary outcome to test for any carry-over effects, by adding a treatment by period interaction term.
  - First Week of Data: The primary and secondary hierarchical CGM analyses will be repeated without excluding the first week of CGM data.

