Population	 Inclusion Clinical diagnosis, based on investigator assessment, of type 1 diabetes for at least one year and using insulin for at least 1 year Using an insulin pump for at least 3 months (which may include use of automated features) Familiarity and use of a carbohydrate ratio for meal boluses Age ≥18.0 years old For females, not currently known to be pregnant If female and sexually active, must agree to use a form of contraception to prevent pregnancy while a participant in the study. A negative serum or urine pregnancy test will be required for all females of child-bearing potential. Participants who become pregnant will be discontinued from the study. Also, participants who during the study develop and express the intention to become pregnant within the timespan of the study will be discontinued. If using a personal CGM, willingness to use a Dexcom G6 CGM and discontinue personal CGM use during the study; note if the system offers an open-loop mode or can be switched to a PLGS mode that is compatible with the Dexcom G6, the system may be used during the study in these modes only
	• Willingness to switch to lispro (Humalog) or aspart (Novolog) if not using already, and to use no other insulin besides lispro (Humalog) or aspart (Novolog) during the study

	• Willingness not to start any new non-insulin glucose-lowering agent during the course of the trial, and not to use Afrezza during the trial
	• Investigator believes that the participant can successfully and safely operate all study devices and is capable of adhering to the protocol
	Exclusion Criteria
	 Use of Afrezza or any non-insulin glucose-lowering agent other than metformin (including GLP-1 agonists, DPP-4 inhibitors, SGLT-2 inhibitors, sulfonylureas) unless participant is willing to discontinue during the trial.
	 Two or more episodes of DKA requiring an emergency room visit or hospitalization in the past 6 months
	 Two or more episodes of severe hypoglycemia with seizure or loss of consciousness in the last 6 months
	4) Hemophilia or any other bleeding disorder
	5) A medical or other condition that in the opinion of the investigator could create a safety concern for the participant or put the study at risk
	 a. History of frequent severe hypoglycemia or history of frequent severe hyperglycemia and/or ketosis, without emergency room visit or hospitalization, due to poor diabetes self-management may be disqualifying per investigator judgment

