- of a severe allergic reaction or asthma attack in addition to use of oral or injectable
- 566 glucocorticoids to determine if closed-loop use should be temporarily discontinued.
- 567 Participants will be specifically instructed:
- 568 1) Not to upgrade the phone operating system or the iAPS app will no longer allow closed 569 loop operation.
- 570 2) Not to plug headphones into the study phone or alerts will be silenced.
- 571 3) Not to put the phone on vibrate mode or alerts will be silenced.
- 572 4) Not to use any manufacturer provided (e.g. Dexcom G6 Mobile App) or third-party
 573 components for CGM connectivity and monitoring, as this will interfere with
 574 connectivity to the study phone.
- 575 After study system training has been completed, participants in Group A will proceed with home
- 576 use of the study system. Participants may use the study pump and study phone without closed-
- 577 loop and study CGM during periods of component disconnections or technical difficulties.

578 **5.4.5 SAP Training and Device Use**

- 579 During the SAP period, participants will use their own insulin pump and the study Dexcom G6
- sensor. If a participant is using a home pump with PLGS capability compatible with the study
- sensor, he/she may keep the pump in PLGS mode; however, an AID system cannot be used.
- 582 All participants will have used a pump and sensor either prior to enrolling in the study or during
- 583 the CGM run-in phase. Study staff will review use of pump and sensor therapy in diabetes self-
- 584 management, uploading of device data as needed, and reviewing of data visualizations.
- 585 Participants may use available Dexcom software and features of the study CGM related to
- 586 mobile data access or remote monitoring, but will be instructed not to use any third-party
- 587 components for this purpose.

589 Chapter 6: Crossover Trial Home Procedures

590 **6.1 Guidance on Clinical Staff Contact**

591 Participants will be provided with contact information and will be asked to call the study clinical

592 staff for any health-related issues and for technical issues with any study-provided device.

- 593 Questions relating to the study protocol will be dealt with by a study staff member on call.
- 594 Participants will be referred to their own medical providers for issues not directly related to the
- 595 study and to local Emergency Medical Services for medical emergencies

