- 629 pump settings, but instead to try to limit changes to safety concerns only.

630 6.2.6 Hypoglycemia Safety Protocol

- 631 During the course of the study, participants will be permitted to change the CGM low glucose 632 threshold alert setting on their device or mobile app (as applicable), but will be instructed to
- 633 choose a value no less than 60 mg/dL.
- 634 If a participant receives a CGM hypoglycemia threshold or predictive alarm or notes that the
- 635 CGM glucose is below the hypoglycemia threshold alarm value, confirmatory fingerstick testing
- 636 will be performed if required by CGM labeling and the participant will be instructed to treat
- 637 hypoglycemia with ~15 grams of fast-acting oral glucose.

638 6.2.7 Hyperglycemia Safety Protocol

During the course of the study, participants will be permitted to change the CGM high glucose

- threshold alert setting on their device or mobile app (as applicable), but will be instructed tochoose a value no greater than 300 mg/dL.
- 642 If a participant receives a CGM hyperglycemia threshold alarm or notes that the CGM glucose
- 643 is above the hyperglycemia threshold alarm value, confirmatory fingerstick testing will be
- 644 performed if required by CGM labeling.
- 645 If a participant's CGM reading is >300 mg/dL for over 2 hours or $\ge 400 \text{ mg/dL}$ at any point, the 646 participant will be instructed to take the following steps:
- Perform a blood glucose meter check.
- If the blood glucose is >300 mg/dL, check for blood ketones with the study ketone meter.
- If the ketone level is >0.6 mmol/L, take correction insulin, change insulin (pump) infusion site and contact study staff.
- If a participant administers correction insulin via insulin syringe, participants will be instructed to disable closed-loop control for approximately four hours.

653 **6.2.8 Device Data Uploads**

- The study system phones will include a study-supplied SIM card (if personal SIM card is not
- being used) to ensure near continuous automatic upload of data to the remote monitoring system.
- During the SAP study period, participants will be asked to upload CGM data (and pump data, if
- 657 possible) prior to each scheduled phone call or clinic visit.

658 **6.2.9 Remote Monitoring**

- 659 During the 2-week Pilot Phase, subjects will have real-time event-based remote monitoring alerts
- present from the study phone to notify study staff of prolonged periods of hypoglycemia (>30

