689 Protocol Chair to perform the visit remotely

690 Additional contacts or visits may occur as needed.

691 7.2 Procedures at Phone Contacts and Follow-up Visits

692 7.2.1 Phone Contacts

693 Prior to each phone contact, the participant will be asked to upload device data as described in 694 section 6.2.8 for study staff review. During the phone call, study staff will:

- Assess compliance with study device use
- Answer questions about using the study system
- Assess adverse events, adverse device effects, and device issues
- Review glycemic control
- 699 Phone contacts may be performed via videoconference at investigator discretion.

700 7.2.2 Procedures Performed During Each Follow-up Visit

- 701 The following procedures will be done at all visits in both periods, unless otherwise stated
- Assessment of compliance with study device use
- Retraining on system use as needed

704	• Assessment of adverse events, adverse device effects, and device issues
705 706 707	• Download of CGM data (when available), blood glucose meter data, and blood ketone meter data (for videoconferences, participant upload of any devices that supports cloud upload, and subsequent download by clinic staff)
708 709	• During clinic visits, QC test blood glucose meter with the available concentration(s) of control solution if the meter is brought to the visit (except for 13-week visit of period 2)
710 711	In addition, the following will be done at the 13-week visit in each period, unless otherwise stated:
712 713 714	• Urine pregnancy test for females of child-bearing potential (period 1 only); for videoconferences, test can be performed at home with a study-provided kit and verbal report of test result
715 716	• Participant weight, height, and blood pressure and pulse; for videoconferences, a verbal report of the participant's weight and height will be acceptable
717 718 719	• Collection of a blood sample to send to the central laboratory for HbA1c determination; for videoconferences, a capillary sample may be obtained at home with a study-provided kit and mailed to the central laboratory
720	Completion of the following questionnaires:
721	 Diabetes Distress Scale
722	Glucose Monitoring Satisfaction Survey
723	 Hypoglycemia Confidence
724	 Diabetes Technology Attitudes
725	 INSPIRE Survey (following study system period only)
726	 System Usability Scale Survey (SUS) (following study system period only)
727	Return study devices as appropriate

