#### **Randomized Crossover Trial**

Eligible participants will be randomly assigned to one of two treatment groups for 13 weeks each:

- 1. Group A: study system for period 1 for 13 weeks, then SAP for period 2 for 13 weeks
- 2. Group B: SAP for period 1 for 13 weeks, then study system for Period 2 for 13 weeks

Study System Period: The participant will be trained regarding AID study system use including meal announcement, meal bolusing, correction doses, and exercise. Participants will be expected to use the study system at all times at home with the exception of times of illness.

SAP Period: During the SAP period, participants will use their own insulin pump and a study-provided Dexcom G6 sensor.

• PLGS mode on the pump can be used if feasible but an AID system cannot be used.

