416 417 418	
 
Flow chart accounting for all participants at all scheduled visits and phone contacts post treatment initiation to assess visit and phone completion rates – will include missing, in and out of window visit and phone contacts
 

419	
 
Number of and reasons for unscheduled visits and phone calls
 

420 421	
 
Number of participants who stopped treatment and reasons
 

422	12. Baseline Descriptive Statistics
423 424 425 426	Baseline demographic and clinical characteristics of the cohort of all randomized participants will be summarized in a table using summary statistics appropriate to the distribution of each variable. Will include:
427	• Age
428	• Gender
429	• Race/ethnicity
430	
 
Income, education, and/or insurance status
 

431	
 
Diabetes duration
 

432	
 
Daily SMBG at enrollment
 

433	• HbA1c

434	• BMI
435	• C-peptide
436	• Participant-reported number of SH and DKA 12 months prior to the start of the study
437 438	
439 440	13. Other Tabulations
441	Individual listings for each participant will include the following:
442	• Treatment period order, age, gender, race/ethnicity, duration, height, weight, and BMI
443 444	• Study related information (like enrollment and randomization dates, enrollment and randomization HbA1c, randomization C-peptide, status, run-in requirement)
445	
 
Previous SMBG use, non-insulin medications, devices months used and manufacturer
 

446	Past SH and DKA events
447	
 
Physical exam results
 

448	
 
Income, education, and insurance
 

449	
 
Pre-existing medical conditions other than diabetes
 

450	
 
Medication at enrollment
 

451	Baseline glucose metrics
452 453	The following tabulations and analyses will be performed by treatment period:
454	
 
Percent sensor use – overall and by month
 

455	• The daily frequency of downloaded SBGM use - overall and by month
456 457	The following tabulations and analyses will be performed for MPC period only:
458	
 
Percent time in different operational modes - overall and by month
 

459	Percent change of clinical and controller adaptation parameters throughout closed-loop use
460 461	
 
Rate of different failure events and alarms per 24 hours recorded by the system – overall and by month
 

462 463 464 465	14. Planned Interim Analyses
466	

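### The >80% per-protocol set checks only sensor wear in the sensor-augmented-pump period, so prohibited personal closed-loop use there does not remove a participant

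*SAP*

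**What the plan says.** Here "SAP period" means the sensor-augmented-pump treatment period, and "analysis plan" means the SAP document.

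- **Per-protocol rule.** Analysis plan section 6.2 repeats the primary and hierarchical analyses in participants who "used the system in CL mode for >80% (i.e. >1,613 hours) during the MPC period" and who "used the sensor for >80% (i.e. >1,613 hours) during the SAP period". Protocol 12.5.1 has the same pair of >80% conditions, for the primary analysis only.
- **Comparator.** Protocol 5.4.5 says of a participant whose home pump has compatible predictive low-glucose suspend (PLGS) that "he/she may keep the pump in PLGS mode; however, an AID system cannot be used". Analysis plan Table 1 repeats it: "PLGS mode on the pump can be used if feasible but an AID system cannot be used".
- **Who may enter.** The inclusion criteria (Protocol Summary and 2.2.1) read "Using an insulin pump for at least 3 months (which may include use of automated features". Current AID users may enrol if willing to stop closed-loop use, and may keep a G6-compatible system in open-loop or PLGS mode.
- **Data on pump mode.** In the SAP period, under Protocol 6.2.8, "participants will be asked to upload CGM data (and pump data, if" possible, before every scheduled call or visit. The visit list in Protocol 7.2.2 has "Download of CGM data (when available), blood glucose meter data, and blood ketone meter data" and does not name the personal pump. Analysis plan section 13 lists "Percent time in different operational modes - overall and by month" for the MPC period only, as does Protocol 12.9.
- **Status of the analysis.** Sections 6.1 and 6.2 of the analysis plan put the primary and hierarchical tests on the intention-to-treat principle. The per-protocol analyses are replications.

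**The concern.** The two halves of the rule test different things. In the MPC period the rule tests delivery of the assigned treatment. In the SAP period it tests whether a sensor was worn, which is needed for the outcome but does not show that the comparator was followed. What separates the comparator from the intervention is the absence of closed-loop control, and the rule does not ask about it.

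Closed loop runs on sensor data, so using it does not reduce sensor wear. The breach is foreseeable: some participants may own an AID-capable pump, and they use their own pump at home for 13 weeks. If it happens, a per-protocol set that keeps those participants cannot show whether the contrast changes when the comparator is delivered as planned. The report would also not show how SAP-period time divided between open loop, PLGS and any AID, because mode is tabulated for the other period only.

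**Working it through.** **1. The plan's own figures.**
- Threshold: 0.80 × 12 weeks × 168 h = 1,612.8 h, which matches the stated 1,613 h.
- Sample size (analysis plan section 4): effect 8 points, SD 17, correlation 0.70, two-sided 0.05, power 90%. SD of the paired difference = 17 × √(2 × (1 − 0.70)) = 13.17. The normal approximation gives (1.960 + 1.282)² × 13.17² / 8² = 28.5, so 29. The paired t calculation gives 31 (power 0.905), the stated N.

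The per-protocol gap changes neither figure.

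**2. Does the rule keep such a participant?** Take someone with closed loop >80% in the MPC period who, in the SAP period, runs a personal AID on the G6 with sensor wear >80%. Both conditions are met and no third condition applies, so the participant is kept.

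**3. Time in range.** The documents give neither the effect of personal AID nor the share of prior AID users. Assume the planned effect of 8 points.
- Shrinkage = share of SAP person-time on AID × 8.
- 10% of person-time: 0.10 × 8 = 0.8 points, leaving 7.2.
- 3 of 35 participants throughout: 3/35 × 8 = 0.69 points.

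For scale, with the plan's SD and correlation and 32 participants, paired-t power is 91% at 8 points and 85% at 7.2. That loss would come from the AID use itself. The per-protocol rule does not cause it; it only fails to show it.

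**4. Time below 54 mg/dL.** The contrast is MPC minus SAP, with a limit of +1.0 point and one-sided 0.025 (analysis plan section 8.1). Let f be the share of analysed participants on AID throughout the SAP period, and a the AID-minus-SAP effect on time below 54. The contrast then shifts by −f × a.

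Assumptions, none given in the documents: n = 32; 1 to 6 participants affected; SD of the paired difference 0.5 to 2 points; a = −0.1 to −0.5 in the direction the documents expect, and a = +0.3 as the opposite case.

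| Case | Shift in MPC − SAP | False non-inferiority rate at true difference +1.0 (2.5% without AID use) |
|---|---|---|
| a = −0.1, 1 of 32 | +0.003 | 2.3% to 2.45% |
| a = −0.5, 6 of 32 | +0.094 | 0.14% to 1.3% |
| a = +0.3, 1 of 32 | −0.009 | 2.65% to 3.16% |
| a = +0.3, 6 of 32 | −0.056 | 3.6% to 9.0% |

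The range within each row is over the assumed SDs. With a true difference of 0 and SD 2, the chance of showing non-inferiority is 78.2% without AID use. It falls to between 78.0% (a = −0.1, 1 of 32) and 70.0% (a = −0.5, 6 of 32).

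**5. Which sign of a do the documents support?** Protocol 1.4.3 judges it more likely that the intervention lowers both hypoglycemia and hyperglycemia. Protocol 1.1.1 reports daytime hypoglycemia falling from 5.0% to 1.9% in an earlier three-month study of the same control approach. Both point to negative a for closed-loop control. Neither measures a personal AID system against SAP on time below 54.

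**The case against.** **A reader might infer that the gap tilts the non-inferiority check towards success**, by the usual argument that contamination pulls a contrast to zero. The documents do not support that. A pull to zero helps non-inferiority only when the new treatment is truly worse and the contaminating treatment shares the harm. On the documents' expectation, AID in the SAP period lowers control time below 54, moves MPC minus SAP up towards the limit, and makes non-inferiority harder to show. The time-in-range gate adds to this, since the same use shrinks the difference that must be significant first. Protocol 1.4.3 does acknowledge that automated dosing could increase hypoglycemia, so the opposite case is possible, but only conditionally.

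**Formal inference does not use this set.** This stands. The analysis is supportive and carries no decision rule. The documents do not say it was designed to protect the non-inferiority test.

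**Controls and data exist.** This stands in part. Willingness not to use personal AID is an inclusion criterion. Device compliance is assessed at each contact, although the wording concerns study devices and the SAP-period pump is personal. Non-compliance is a deviation, and deviations are tabulated by period with descriptions, so identified AID use should be visible. Pump data are requested before each call and visit, and the visit schedule has a generic device-download row. It would be wrong to say that no pump data are sought. However, the request is conditional, and deviations do not define the per-protocol set.

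**The loophole is narrower than any AID use.** This stands. Participants must wear the study G6, so someone running an AID on another sensor would miss the threshold unless they wore both.

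**Conclusion.** The point holds as a gap in a supportive analysis. As written, the >80% set keeps a participant who used a prohibited G6-compatible personal AID in the SAP period, provided the MPC-period criterion is met, so the set does not isolate MPC versus SAP.

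Its effect on time in range is 0.8 points per 10% of SAP person-time on AID, if personal AID has an 8-point effect. For time below 54 mg/dL the direction depends on what AID does to that outcome. The shift is at most about 0.09 points over the assumed range in the expected direction, against a limit of 1.0, and it works against non-inferiority. Only if AID raises time below 54 does it favour non-inferiority.

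The number of participants who could be affected is unknown, because the documents do not give the share of AID users. The formal intention-to-treat tests are not affected by the rule. Minor priority.

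**What to change.** - **Analysis plan section 6.2** (and Protocol 12.5.1 for consistency): add to the >80% set the condition of no documented use of an automated closed-loop mode in the SAP period. Take this from the pump data already requested or, where these are unavailable, from one pump-mode question on the case report form. PLGS remains allowed, as the protocol states.
- **Analysis plan section 13:** tabulate pump mode (open loop, PLGS, AID) for the SAP period as well as operational mode for the MPC period.
- **Reporting:** state with the per-protocol result that the direction of any bias in time below 54 depends on the effect of AID on that outcome, and is expected to be against non-inferiority.

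The cost is a few lines of wording, one form item and one table. The downside is a slightly smaller per-protocol set and some reliance on self-report where pump data cannot be obtained.
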